7.1 Derived and Transformed Data

Details on derivations and transformations for each individual study are specified in the study SAPs. The study teams have worked closely to ensure consistent algorithms were implemented across studies. Modifications to study algorithms are not planned for data integration. In the rare instance where modifications to specific algorithms are necessary to facilitate programming, documentation will be provided in the data definition tables and reviewer's guide.

7.2 Treatment Assignments and Analysis Groups

Treatment will be assigned using the treatment assignments from the individual studies.

Integrated listings will display the treatment received at the time the data was collected.

The following treatment/analysis groups will be included in summary tables, in the order shown:

- Placebo
- 340 mg ADS-5102
- \geq 340 mg ADS-5102
- ADS-5102

Individual summaries for 260 mg ADS-5102 and 420 mg ADS-5102 will not be included, but are available in the study results for ADS-PAR-AM201.

Since subjects may have received more than one treatment or ADS-5102 dose-level, they may be counted multiple times in summary tables, but will appear at most once in each treatment/analysis group and at most once in the overall column (where displayed).

7.3 Subject Identification

The Unique Subject Identifier (USUBJID) is unique for all subjects for every study in which they participated and is used to identify subjects in the analysis database. A truncated version of this identifier will be displayed in data listings. Since this identifier was not displayed in the individual study results, a listing will be provided displaying this value along with the subject identifier displayed in the individual study results.

7.4 Coding Dictionaries

Integrated concomitant medication data will be recoded using World Health Organization (WHO) Drug Dictionary dated March, 2014.

Integrated adverse event data will be recoded using Medical Dictionary for Regulatory Activities (MedDRA®) version 17.0.

7.5 Subgroup Definitions

The following subgroups will be explored for key safety analyses:

- Gender
- Age ($<65, \ge 65, \ge 65$ to $<75, \ge 75$)
- Race (white, non-white)
- Baseline renal function (estimated GRF \leq 60 or estimated GFR \geq 60)
- Weight (< or \ge median)
- Baseline MAO-B inhibitor medications (Yes, No)
- Baseline Dopamine Agonist medications (Yes, No)
- Baseline levodopa dose (< or ≥ median)
- Time since PD diagnosis in years (< or \ge median)
- Age at PD diagnosis (< or \ge median)
- Prior Deep Brain Stimulation (Yes, No)
- Geographic Region (European Union vs North American)

For subgroups categorizations based on median values, a value for each treatment/analysis group will be calculated and subjects will be categorized separately for each treatment/analysis group in which they are included.

7.6 Definitions of Baseline, Analysis Day 1, and Study Day 1

The baseline assessment will be the last available assessment prior to the first dose of study medication for a particular treatment. For subjects receiving multiple treatments, baseline assessments will be defined for each treatment assignment. For subjects receiving 340 mg ADS-5102 in more than one study, the following logic will be applied to assign the baseline value:

- For subjects continuing into ADS-AMT-PD302 with no gap in treatment prior to enrollment, the baseline assessment will be the last available assessment prior to the first dose of 340 mg ADS-5102 in any study.
- For subjects continuing in ADS-AMT-PD302 with a gap in treatment prior to enrollment, the baseline assessment will be the last available assessment prior to the first dose of 340 mg ADS-5102 in ADS-AMT-PD302. Assessments from the first study in which the subject enrolled will not be considered for assignment as baseline.

An overall baseline value will be determined and used in summaries were overall values are calculated and displayed. This value will be assigned following the same logic outlined previously, but study treatment will not be considered in the selection of this value.

Analysis Day 1 is defined as the date of the baseline visit. Subjects should be dispensed the study drug at the baseline visit and presumably take the first dose at bedtime on the same day. No Day 0 is defined. Negative study days indicate observations were obtained prior to treatment.

Study Day 1 is defined as the date of the first dose of study drug for the individual study in which the subject participated.

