9.2.8 Adverse Events of Special Interest

Adverse events of special interest are grouped into three event categories: Neuropsychiatric (CNS), Falls, and Hallucinations. The CNS category combines the following SOCs: Nervous system disorder and Psychiatric disorder. The Falls category combines all PTs that contain the term "Fall" or "Falls". The Hallucinations category combines all PTs that contain the term "Hallucination".

Event incidence will be summarized treatment/analysis group.

Time to onset will be analyzed and is defined as the number of days from the first dose of study drug to the onset of the first AE in the category. Subjects will be censored at the latest date known not to have had such AE. The median time to event and the associated 95% confidence interval for the Placebo and 340 mg ADS-5102 treatment groups will be estimated using the Kaplan-Meier method. Kaplan-Meier estimates of the survival function will be calculated and displayed graphically.

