ge at start of levodopa treatment (yrs)					
n	XX	XX	XX	XX	XX
Mean	XX.X	XX.X	XX.X	XX.X	XX.X
SD	XX.XX	XX.XX	XX.XX	XX.XX	XX.XX
Median	XX.X	XX.X	XX.X	XX.X	XX.X
Min, Max	XX, XX				

Note: Durations calculated using diagnosis/start/onset dates.

Source Data: Listing 2.3.1

<DIRECTORY PATH>PROGRAM NAME Executed: DDMMMYYYY hh:mm

Table 1.3.1
Parkinson's Disease History
Safety Population

		340mg ADS-5102 (N=xx)	≥340mg ADS-5102 (N=xx)	ADS-5102 (N=xx)	All (N=xx)
	Placebo (N=xx)				
Duration of levodopa treatment (yrs)					
N	XX	XX	XX	XX	XX
Mean	XX.X	XX.X	XX.X	XX.X	XX.X
SD	XX.XX	XX.XX	XX.XX	XX.XX	xx.xx
Median	XX.X	XX.X	XX.X	XX.X	XX.X
Min, Max	XX, XX	xx, xx	XX, XX	xx, xx	XX, XX
Duration of levodopa-induced dyskinesia					
N	XX	XX	XX	XX	XX
Mean	XX.X	XX.X	XX.X	XX.X	XX.X
SD	XX.XX	XX.XX	XX.XX	XX.XX	XX.XX
Median	XX.X	XX.X	XX.X	XX.X	XX.X
Min, Max	XX, XX	XX, XX	xx, xx	xx, xx	XX, XX
Baseline levodopa (any preparation) dose (mg)					
n	XX	XX	XX	XX	XX
Mean	XX.X	XX.X	XX.X	XX.X	XX.X
SD	XX.XX	XX.XX	XX.XX	XX.XX	XX.XX
Median	XX.X	XX.X	XX.X	XX.X	XX.X
Min, Max	XX, XX	XX, XX	xx, xx	xx, xx	XX, XX
< median n (%)	xx (xx.x)	xx (xx.x)	xx (xx.x)	xx (xx.x)	xx (xx.x)
≥ median n (%)	xx (xx.x)	xx (xx.x)	xx (xx.x)	xx (xx.x)	xx (xx.x)

Note: Durations calculated using diagnosis/start/onset dates.

Source Data: Listing 2.3.1

Table 1.3.2
Parkinson's Disease Related Baseline Characteristics
Safety Population

	340mg ≥340mg						
	Placebo (N=xx)	ADS-5102 (N=xx)	ADS-5102 (N=xx)	ADS-5102 (N=xx)	All (N=xx)		
MDS-UPDRS: Part I							
n	XX	XX	XX	XX	XX		
Mean	XX.X	XX.X	XX.X	XX.X	xx.x		
SD	XX.XX	XX.XX	XX.XX	XX.XX	XX.XX		
Median	XX.X	XX.X	XX.X	XX.X	xx.x		
Min, Max	xx, xx	xx, xx	xx, xx	xx, xx	XX, XX		
MDS-UPDRS: Part II							
n	XX	XX	XX	XX	XX		
Mean	XX.X	XX.X	XX.X	XX.X	XX.X		
SD	XX.XX	XX.XX	XX.XX	XX.XX	XX.XX		
Median	XX.X	XX.X	XX.X	XX.X	XX.X		
Min, Max	xx, xx	xx, xx	XX, XX	XX, XX	XX, XX		
MDS-UPDRS: Part III							
n	XX	XX	XX	XX	XX		
Mean	XX.X	XX.X	XX.X	XX.X	XX.X		
SD	XX.XX	XX.XX	XX.XX	XX.XX	XX.XX		
Median	XX.X	XX.X	XX.X	XX.X	XX.X		
Min, Max	XX, XX	XX, XX	xx, xx	xx, xx	XX, XX		
MDS-UPDRS: Combined (Part I, II, and III)							
n	XX	XX	XX	XX	XX		
Mean	XX.X	XX.X	XX.X	XX.X	XX.X		
SD	XX.XX	XX.XX	XX.XX	XX.XX	XX.XX		
Median	XX.X	XX.X	XX.X	XX.X	XX.X		
Min, Max	XX, XX	XX, XX	XX, XX	XX, XX	XX, X		

Source Data: Listings 2.3.2, 2.3.3

Table 1.3.2
Parkinson's Disease Related Baseline Characteristics
Safety Population

		340mg	≥340mg	ADS-5102 (N=xx)	All (N=xx)
	Placebo (N=xx)	ADS-5102 (N=xx)	ADS-5102 (N=xx)		

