Table 1.6.10.2

Kaplan-Meier Analysis of Time to Onset of AE (Neuropsychiatric)

Safety Population

	Placebo	340 mg ADS-5102
	(N=xx)	(N=xx)
Days to onset of first AE: Neuropsychiatric		
Event n(%)	xx (xx.x)	xx (xx.x)
10th percentile (days)	XX.X	XX.X
25 th percentile (days)	XX.X	XX.X
50th percentile (days)	XX.X	XX.X
75 th percentile (days)	XX.X	XX.X
90th percentile (days)	XX.X	XX.X
Min - Max	xx.x - xx.x	xx.x - xx.x
edian (days)		
Estimate	XX.X	XX.X
95% CI	x.xx, x.xx	x.xx, x.xx

Note: Percentages are calculated out of the number of subjects in each treatment group. "+" in MIN - MAX means censored value. AEs are coded using MedDRA Version 17.0. NE = Non-estimable.

Note: The Neuropsychiatric category combines the following System of Organs: Nervous system disorder and Psychiatric disorder. Subjects will be censored at their last contact date if no AE (Neuropsychiatric) occurred.

Source Data: Listing 2.6.1

<DIRECTORY PATH>PROGRAM NAME Executed: DDMMMYYYY hh:mm

Programming Note: Some percentiles will be non-estimable. When this occurs, use " NE^{1} "

Table 1.6.10.3

Kaplan-Meier Analysis of Time to Onset of AE (Neuropsychiatric) by Gender Safety Population

	Placebo	340 mg ADS-5102
	(N=xx)	(N=xx)
Days to onset of first AE: Neuropsychiatric		
Event n(%)	xx (xx.x)	xx (xx.x)
10th percentile (days)	XX.X	xx.x
25 th percentile (days)	XX.X	xx.x
50th percentile (days)	XX.X	xx.x
75 th percentile (days)	XX.X	xx.x
90 th percentile (days)	XX.X	XX.X
Min - Max	xx.x - xx.x	xx.x - xx.x
Median (days)		
Estimate	XX.X	XX.X
95% CI	X.XX, X.XX	x.xx, x.xx

Note: Percentages are calculated out of the number of subjects in each treatment group. "+" in MIN - MAX means censored value. AEs are coded using MedDRA Version 17.0. NE = Non-estimable.

Note: The Neuropsychiatric category combines the following System of Organs: Nervous system disorder and Psychiatric disorder. Subjects will be censored at their last contact date if no AE (Neuropsychiatric) occurred.

Source Data: Listing 2.6.1

<DIRECTORY PATH>PROGRAM NAME Executed: DDMMMYYYY hh:mm

Programming Note: Some percentiles will be non-estimable. When this occurs, use " NE^{1} "

Gender: Male

Min - Max

340 mg ADS-5102 (N=xx)

> xx (xx.x) xx.x

> > XX.X

XX.X

XX.X

XX.X

xx.x - xx.x

XX.X

XX.X

XX.X

xx.x - xx.x

Table 1.6.10.3

Kaplan-Meier Analysis of Time to Onset of AE (Neuropsychiatric) by Gender Safety Population

	Placebo
	(N=xx)
Days to onset of first AE: Neuropsychiatric	
Event n(%)	xx (xx.x)

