Note: The Neuropsychiatric category combines the following System of Organs: Nervous system disorder and Psychiatric disorder. Subjects will be censored at their last contact date if no AE (Neuropsychiatric) occurred.

Source Data: Listing 2.6.1

<DIRECTORY PATH>PROGRAM NAME Executed: DDMMMYYYY hh:mm

Table 1.6.10.7

Kaplan-Meier Analysis of Time to Onset of AE (Neuropsychiatric) by Weight Safety Population

Repeat of 1.6.10.3

Weight:

- 1. < median
- 2. ≥ median

Note: Percentages are calculated out of the number of subjects in each treatment group. "+" in MIN - MAX means censored value. AEs are coded using MedDRA Version 17.0. NE = Non-estimable.

Note: The Neuropsychiatric category combines the following System of Organs: Nervous system disorder and Psychiatric disorder. Subjects will be censored at their last contact date if no AE (Neuropsychiatric) occurred.

Source Data: Listing 2.6.1

Kaplan-Meier Analysis of Time to Onset of AE (Neuropsychiatric) by Baseline MAO-B Inhibitor Medications
Safety Population

Repeat of 1.6.10.3

Baseline MAO-B Inhibitors:

- 1. Yes
- 2. No

Note: Percentages are calculated out of the number of subjects in each treatment group. "+" in MIN - MAX means censored value. AEs are coded using MedDRA Version 17.0. NE = Non-estimable.

Note: The Neuropsychiatric category combines the following System of Organs: Nervous system disorder and Psychiatric disorder. Subjects will be censored at their last contact date if no AE (Neuropsychiatric) occurred.

Source Data: Listing 2.6.1

<DIRECTORY PATH>PROGRAM NAME Executed: DDMMMYYYY hh:mm

Table 1.6.10.9

Kaplan-Meier Analysis of Time to Onset of AE (Neuropsychiatric) by Baseline Dopamine Agonist Medications
Safety Population

Repeat of 1.6.10.3

Baseline Dopamine Agonist Medications:

- 1. Yes
- 2. No

Note: Percentages are calculated out of the number of subjects in each treatment group. "+" in MIN - MAX means censored value. AEs are coded using MedDRA Version 17.0. NE = Non-estimable.

Note: The Neuropsychiatric category combines the following System of Organs: Nervous system disorder and Psychiatric disorder. Subjects will be censored at their last contact date if no AE (Neuropsychiatric) occurred.

Source Data: Listing 2.6.1

Kaplan-Meier Analysis of Time to Onset of AE (Neuropsychiatric) by Baseline Levodopa Dose Safety Population

Repeat of 1.6.10.3

Baseline Levodopa Dose:

- 1. < median
- 2. ≥ median

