Note: Percentages are calculated out of the number of subjects in each treatment group. "+" in MIN - MAX means censored value. AEs are coded using MedDRA Version 17.0. NE = Non-estimable.

Note: The Falls category combines all Preferred Terms that contain the terms "Fall" or "Falls". Subjects will be censored at their last contact date if no AE (Falls) occurred.

Source Data: Listing 2.6.1

Kaplan-Meier Analysis of Time to Onset of AE (Falls) by Baseline Dopamine Agonist Medications
Safety Population

Repeat of 1.6.10.3

Baseline Dopamine Agonist Medications:

- 1. Yes
- 2. No

Note: Percentages are calculated out of the number of subjects in each treatment group. "+" in MIN - MAX means censored value. AEs are coded using MedDRA Version 17.0. NE = Non-estimable.

Note: The Falls category combines all Preferred Terms that contain the terms "Fall" or "Falls". Subjects will be censored at their last contact date if no AE (Falls) occurred.

Source Data: Listing 2.6.1

<DIRECTORY PATH>PROGRAM NAME Executed: DDMMMYYYY hh:mm

Table 1.6.11.10

Kaplan-Meier Analysis of Time to Onset of AE (Falls) by Baseline Levodopa Dose Safety Population

Repeat of 1.6.10.3

Baseline Levodopa Dose:

- 1. < median
- 2. ≥ median

Note: Percentages are calculated out of the number of subjects in each treatment group. "+" in MIN - MAX means censored value. AEs are coded using MedDRA Version 17.0. NE = Non-estimable.

Note: The Falls category combines all Preferred Terms that contain the terms "Fall" or "Falls". Subjects will be censored at their last contact date if no AE (Falls) occurred.

Source Data: Listing 2.6.1

Kaplan-Meier Analysis of Time to Onset of AE (Falls) Time since PD Diagnosis in Years
Safety Population

Repeat of 1.6.10.3

Time since PD Diagnosis in Years:

- 1. < median
- 2. ≥ median

Note: Percentages are calculated out of the number of subjects in each treatment group. "+" in MIN - MAX means censored value. AEs are coded using MedDRA Version 17.0. NE = Non-estimable.

Note: The Falls category combines all Preferred Terms that contain the terms "Fall" or "Falls". Subjects will be censored at their last contact date if no AE (Falls) occurred.

Source Data: Listing 2.6.1

<DIRECTORY PATH>PROGRAM NAME Executed: DDMMMYYYY hh:mm

Table 1.6.11.12

Kaplan-Meier Analysis of Time to Onset of AE (Falls) by Age at PD Diagnosis
Safety Population

Repeat of 1.6.10.3

Age at PD Diagnosis:

- 1. < median
- 2. \ge median

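### Four subgroup factors are split at each treatment group's own median, so one stratum label in the Kaplan-Meier tables can cover different ranges for Placebo and 340 mg (minor).

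*SAP*

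**What the plan says.** SAP 7.5 lists 12 subgroup factors. Four are split at a median: weight, baseline levodopa dose, time since PD diagnosis and age at PD diagnosis. For these, "a value for each treatment/analysis group will be calculated and subjects will be categorized separately for each treatment/analysis group in which they are included". No other section sets a common cut-point.

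SAP 9.2.8 plans the median time to onset of each adverse event category "for the Placebo and 340 mg ADS-5102 treatment groups will be estimated using the Kaplan-Meier method". The subgroup layout is the Table 1.6.10.3 shell, "Kaplan-Meier Analysis of Time to Onset of AE (Neuropsychiatric) by Gender Safety Population". It has one page per stratum, with Placebo and 340 mg as adjacent columns. The shells for the median-split factors, such as "Kaplan-Meier Analysis of Time to Onset of AE (Neuropsychiatric) by Weight Safety Population" and "Kaplan-Meier Analysis of Time to Onset of AE (Falls) by Baseline Levodopa Dose Safety Population", repeat that layout. Their strata are labelled only as below, or at or above, the median. No value is printed, and no note says that the value depends on the column.

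Tables 1.2 and 1.3.1 give n, mean, SD, median and range by column for all four factors, followed by counts below and at or above the median. The row block headed "Baseline levodopa (any preparation) dose (mg)" in Table 1.3.1 is one example.

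SAP 7.6 makes baseline specific to treatment: "For subjects receiving multiple treatments, baseline assessments will be defined for each treatment assignment". It also defines a baseline that ignores treatment: "An overall baseline value will be determined and used in summaries were overall values are calculated and displayed".

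**The concern.** A reader who sees two columns under one stratum label takes them to hold the same kind of subject. With column-specific cuts that need not be so, and the table does not show whether it is.

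Equal medians should not be assumed. The 340 mg column adds open-label ADS-AMT-PD302 subjects to the randomised ones. These include Group 3 (prior DBS), who were never on placebo.

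Subjects who move from placebo to 340 mg appear in both columns (SAP 7.2). Age at diagnosis is fixed for life. Yet a rollover subject whose age at diagnosis lies between the two medians would be in the lower stratum in one column and the upper stratum in the other.

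The rule also takes the information out of the median-split rows of Tables 1.2 and 1.3.1. Apart from ties and missing values, each column is cut at its own middle, so those rows cannot show whether the columns differ.

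What is at stake is how exploratory safety strata read. No error rate is involved.

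**Working it through.** The plan states no figure on this point, so there is nothing to reproduce. The check has two parts: a count of affected outputs and an illustration of size.

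**Outputs**
- Kaplan-Meier tables: 4 factors × 3 event categories (neuropsychiatric, falls, hallucinations) = 12. All repeat the side-by-side shell.
- Kaplan-Meier figures: 12 to match. The note to Figure 3.6.1.1 restricts display to Placebo and 340 mg, and the subgroup figures probably overlay those two groups. The image of Figure 3.6.1.2 is not available, so this is inferred.
- AE overview and SOC/PT tables: 4 factors × 2 families = 8. The pattern shells (1.6.1.2 and 1.6.2.2) print one treatment per page, so the two cuts never share a page.
- Tables 1.2 and 1.3.1: 2.

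**How far apart the medians could be by chance**

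Inputs from SAP section 3: 83 subjects randomised 1:1:1:1, 126 randomised 1:1, and up to 250 in ADS-AMT-PD302.
- Placebo ≈ 83/4 + 126/2 = 20.75 + 63 ≈ 84. Randomised 340 mg is also about 84.
- Earlier subjects: 83 + 126 = 209. Filling ADS-AMT-PD302 to 250 leaves 250 − 209 = 41.

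Assume a normal factor with the same distribution in both columns, and unchanged values for the m subjects who appear in both. With n subjects in the 340 mg column, in SD units:

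SE(gap) = √(π/2) × √(1/84 + 1/n − 2m/(84n))

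A cut gap of d leaves a share 2 × [Φ(d/2) − 0.5] of subjects between the two cuts.

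| Scenario (assumed) | n | m | SE of gap | Share between cuts if gap = SE |
|---|---|---|---|---|
| No rollover | 84 | 0 | 0.193 SD | 7.7% |
| Half of the 125 earlier subjects not on 340 mg roll over | 146 | 42 | 0.137 SD | 5.5% |
| All 209 roll over, 41 in Group 3 | 250 | 84 | 0.111 SD | 4.4% |

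A simulation with independent groups (84 against 84 to 300, 10,000 runs) agrees. With no true difference, the mean absolute gap is 0.12 to 0.15 SD, with 5 to 6% of subjects between the cuts. A true shift of 0.2 SD gives 8 to 9%, and 0.4 SD about 15%. Those shifts are assumed values.

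**What that could do to a displayed risk**

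Assume one logistic risk curve for both columns, with 20 to 30% risk at the placebo median and an odds ratio of 1.5 to 2 per SD. Cut each column at its own median and average the risk within each half. The spurious same-label difference is:
- gap 0.11 SD: 0.6 to 1.8 percentage points
- gap 0.19 SD: 1.0 to 3.1 percentage points

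For comparison, take the standard error of one stratum contrast with 42 placebo subjects against k active subjects, k from 42 (half of 84) to 125 (half of 250), treating columns as independent: √(p(1−p)(1/42 + 1/k)).
- p = 0.2: 8.7 points at k = 42, 7.1 at k = 125
- p = 0.3: 10.0 points at k = 42, 8.2 at k = 125

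Under these assumptions the artefact is smaller than the noise throughout.

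**What a common cut would not change**

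Under SAP 7.6, a no-gap placebo rollover from ADS-AMT-PD301 gets a new baseline for 340 mg about 25 weeks later. Time since diagnosis then rises by 25 × 7/365.25 = 0.48 years, which can move the subject across even a common cut. Of the four factors, only age at diagnosis cannot move.

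**The case against.** The rule is explicit and pre-specified. It is a natural choice where subjects appear in several columns with a baseline for each, and it keeps every column's strata even. The subgroups are exploratory, SAP section 9 plans no formal testing, and 9.2.8 plans no between-group contrast. Tables 1.2 and 1.3.1 print each column's median directly above the split rows, so a reader can recover the cut-points from the same package. A footnote giving them might be enough. All of this stands, and it is why the point is minor. A Kaplan-Meier table should still be readable without a second table to decode its strata, and a footnote would disclose the mismatch without removing it.

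A reader might infer more than the documents support:
- That the medians do differ materially, or that the subgroup results are biased. The documents give no medians, and equal ones remain possible.
- That 4 to 8% of subjects would change stratum under a common cut. That figure is the share lying between the two column medians. A common cut placed between them would move fewer.
- That the eight AE subgroup tables have the same fault. With one treatment per page, each is coherent as it stands.

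**Conclusion.** The point holds as a minor, cheap improvement. Four of the 12 subgroup factors are affected. Twelve Kaplan-Meier tables place two possibly different ranges under one unnumbered label. Twelve figures probably do so too, subject to the missing image. The median-split rows of Tables 1.2 and 1.3.1 are uninformative by construction.

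That labels can differ in meaning follows from the SAP text and shells alone. The size does not: the 0.11 to 0.19 SD and 4 to 8% rest on approximate group sizes, assumed rollover and a normal factor. The 0.6 to 3.1 points also rest on an assumed risk curve. On those assumptions the artefact lies within sampling noise of about 7 to 10 points. The documents do not support a claim of a distorted safety conclusion.

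**What to change.** In SAP 7.5, replace the group-specific medians with one cut-point per factor for all columns: the median of the whole Safety population (the All column), taken at the overall baseline that SAP 7.6 already defines. Print the value in each stratum label, for example Weight < xx kg, including the split rows of Tables 1.2 and 1.3.1. Those rows would then show how the columns differ.

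Cost: one sentence in 7.5, and labels or rows in 12 + 12 + 8 + 2 = 34 outputs. No new data are needed, because the All medians are already planned in Tables 1.2 and 1.3.1. Placebo strata would be slightly less even. Rollover subjects whose value changes between treatment-specific baselines could still change stratum, and confounding from pooling open-label with randomised data would remain.

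If the group-specific rule is kept, the lighter option is to print each column's cut-point on every Kaplan-Meier table and figure.
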